10.1 Analysis

Primary analysis

Percentages in both arms of the study will be compared using binomial regression with a log link, adjusting for the minimization variables to give risk ratios. Risk differences will be estimated similarly. Continuous measures will be compared using linear regression adjusting for minimization variables and baseline measurement of the outcome (where available). Estimates will be given with 95% confidence intervals.

Results will be considered significant at the 5% level. However, attention will be paid to the totality of results and the exact size of the P-value. Smaller values will be treated as stronger evidence against the null hypothesis.

The intention-to-treat principle will be followed in the main analysis, but a secondary per-protocol analysis will also be performed to provide additional information on the nature of the treatment effect.

Subgroup analysis

Subgroup analyses in RCTs mainly serve to investigate possible moderators of the treatment effect – i.e. subgroups of women identifiable at trial entry who will do particularly well or badly with the treatment in question.

Subgroup analyses will only be carried out where there are at least 20 women in each subgroup. Subgroup analyses will be carried out for all minimisation variables.

Two further subgroups analyses are planned, to investigate whether it is possible to identify groups of women for whom hydroxychloroquine would be more or less effective. The first analysis will investigate the way in which aPL was first identified: random testing, recurrent miscarriage, fertility clinic (IVF) or thrombosis. The second will be according to their aPL titre at trial entry: i.e. is it low titre (>95th percentile) alone or according to the Sydney criteria[1].

In each case, the main treatment effect will be assessed in all subgroups, and interaction tests carried out to determine if treatment effect differs significantly between subgroups.

Pharmacokinetics and biomarkers will be investigated in women at St Thomas' only; and will form the focus of a separate study.

Additional points:

 Description of the statistical methods employed – including time(s) for scheduled interim analyses

Statistical methods are described above.

No formal interim analyses are planned. The Data Monitoring Committee will aim to meet in person at least every 6 months, and will consider the results so far. They are empowered to request that the trial stops if there is overwhelming evidence for or against one treatment are such that to randomize further patients would be unethical.

• Procedures for dealing with missing data, unused data and false data. False data may be e.g. interpolated data, and it is not necessarily false

We will follow a four point framework for dealing with incomplete observations which will allow the correct method to be chosen and subsequently implemented.

1. Attempt to follow up all randomized participants, even if they withdraw from allocated treatment

2. Perform a main analysis of all observed data that is valid under a plausible assumption about the missing data. Specifically, we will assume data is missing at random (MAR). Under this assumption, imbalances between treatment groups due to dropout can be corrected by appropriate multiple regression models.

3. Perform a sensitivity analyses to explore the effect of departures from the assumption made in the main analysis. The MNAR (missing not at random) analysis will use the method of White et al. (2011) [28] as implemented in the Stata command rctmiss.

4. Account for all randomized participants, at least in the sensitivity analyses

This framework highlights the importance of using plausible assumptions with regards to the nature of the missing data. These assumptions will then be tested using appropriate sensitivity analyses on observed data using complete cases analysis. For the purpose of the main analysis we will make the assumption that missing data is missing at random and the effect of the intervention is the same in those with and without the observations. Furthermore, checks will be made to ensure that the percentage of missing data within each treatment allocation is not significantly different.

We do not intend to create false data. No duly randomized subjects with outcome data will be excluded. All relevant data collected will be used.

• Procedures for reporting deviations from the original statistical plan

It is not intended to deviate from the data analysis plan as agreed; but if it should prove necessary, the nature, reasons and implications of such deviations for interpreting the results, will be reported to the funders and in any subsequent publications.

• Statement of the trial subjects, whose data will be included in the statistical analysis (e.g. all randomised subjects, all subjects receiving medication, all eligible subjects and all subjects who can be evaluated).

The principal analysis will be according to the intention-to-treat principle, reporting all subjects with analyzable data in their original randomized groups.

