4.2 Trial Design

This is a double blind randomized controlled trial (RCT) of women with aPL planning to fall pregnant, who will be randomized to hydroxychloroquine or an identically looking placebo in addition to their usual medication.

According to our sample size we will enroll 328 pregnant women. In order to achieve this number of patients we will randomize 400 patients.

Our hypothesis is that hydroxychloroquine improves aPL-related pregnancy complications.

The HYPATIA trial has been designed as a multicenter RCT. Participating centers in the UK include Guy's and St Thomas' NHS Foundation Trust, University College London NHS Foundation Trust; the Royal Free London Hospitals, Liverpool Women's Hospital NHS Foundation Trust; Manchester University Hospital, Oxford University Hospital and Cambridge University Hospitals.

In the EU participating centres include: Copenhagen, Hvidovre, Odense, Århus, Ålborg, Sønderborg (all in Denmark), University Hospital Torino/Italy; and Dublin University Hospital/Ireland, Calgary University Hospital/Canada. The HYPATIA trial is supported by an accredited Clinical Trials Unit (King's College London Clinical Trials Unit).

Each center runs a dedicated pregnancy clinic following a routine care protocol for pregnant women with aPL. The patients are closely monitored during their pregnancy and are followed up at least once every trimester, if needed more closely. A visit assessment schedule is outlined in on page 16. The study procedures for the HYPATIA trial are outlined specifically and are almost identical with the standard of care for these patients. We expect all participating sites to follow these study procedures. Data from the routine clinical visits prior to study entry may be used in the HYPATIA study. This includes data from standard of care samples, such as blood results (full blood count, biochemistry, liver profile, auto-antibody status (i.e. Lupus anticoagulant, anti-cardiolipin antibodies, anti- β 2-glycoprotein-I, ENA antibodies).

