6.4.1 Randomisation

Randomisation will be undertaken by the local research team at each site once written informed consent has been obtained, eligibility confirmed, and baseline data collected.

Randomisation is by the method of minimisation, balanced by thrombosis (yes/no), previous adverse pregnancy outcomes (yes/no), previous pregnancy (yes/no), refractory obstetric APS (yes/no) and center.

Randomisation will be performed via a bespoke web-based randomisation system hosted by the King's College London, Clinical Trials Unit (KCTU). This system can be accessed 24 hours a day. Authorised site staff will be allocated a username and password for the system by the Trial Manager. If new staff members join the study, a user-specific username and password must be requested via the Trial Manager from the KCTU team and a request for access to be revoked must be requested when staff members leave the project. Study site staff experiencing issues with system access or functionality should contact the Trial Manager in the first instance.

Once eligibility has been confirmed by recruiting sites, authorised site staff will log into the system by going to www.ctu.co.uk and clicking the link to access the randomisation system. A full audit trail of data entry will be automatically date and time stamped, alongside information about the user making the entry within the system. Staff will enter key information about the patient, including the unique Participant Identification Number (PIN) generated from the Elsevier MACRO electronic data capture (EDC) system after consent. Once a patient is randomised, study drug will be automatically allocated in the system and confirmation emails will be sent to relevant personnel, with appropriate information.

If there are any difficulties in accessing this KCTU website, investigators should call the number below.

https://ctu.co.uk

Telephone: [name] (or e-mail: [contact] or [contact]>)

The investigator, research team, site pharmacy team and the trial manager will be kept blind to the treatment allocation.

Unique pack numbers will be generated for the active and placebo products and will be sent with randomization emails. The trial statistician will know only A vs B, with the meaning of A & B held by the KCTU.

Detailed description of the randomization process: The IMP pack details will be uploaded to the randomization system so the system will know what the production pharmacy has available centrally.

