10.2 Sample Size

The sample size was calculated based on our audit data.

Retrospective data from St Thomas' Hospital showed that treatment with HCQ was associated with a higher rate of live birth (67% in women with SLE and aPL treated with HCQ versus 57% in women in the control group p=0.005) and a lower prevalence of aPL related pregnancy morbidity (47% versus 63% p=0.004).

The HCQ intervention will be added to current standard of care. The trial is powered to detect a 16% reduction in pregnancy morbidity, which is the main outcome of the study (total sample size 328). A minimum of 328 women will therefore be randomized. In order to achieve a number of 328 pregnant women, we will randomize 400 patients. This takes into account those women who do not achieve pregnancy within 12 months and those who do not pregnant due to other reasons.

The calculation was made on the following: significance alpha = 0.05, power 1-beta 80%, percentage cross 5%.

11 Trial Steering Committee

A HYPATIA steering committee has been appointed. The committee includes [name], [name], [name], further HYPATIA study team members and a lay person. A dedicated person from the Clinical Trials Unit will be appointed. An independent chair will be appointed.

The overall role will be to provide overall supervision of the HYPATIA study and the steering committee will meet on a 6 monthly basis. The Steering Committee is the main decision making body. It has overall responsibility for scientific strategy and direction and has ultimate responsibility for ensuring the project's aims are delivered on time and within budget.

12 Data Monitoring Committee

A Data Monitoring Committee has been appointed. The committee includes an independent chair, an independent statistician, the trial statistician and an independent expert.

The DMC has decided the following stopping rules:

Confirmed option of unblinding available at any stage, BUT only if concern that treatment will clearly harm or benefit patients

The simple rule of 3 standard errors will be applied to difference between groups.

13 Direct Access to Source Data and Documents

The Investigator(s) will permit trial-related monitoring, audits, REC review, and regulatory inspections by providing the Sponsor(s), Regulators and REC direct access to source data and other documents (e.g. patients' case sheets, blood test reports, X-ray reports, histology reports etc.).

14 Ethics & Regulatory Approvals

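### The primary log-binomial model, with centre among its adjustment variables, is likely to end on the boundary at the planning risks, where its usual 95% interval is not valid

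*Protocol*

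**What the plan says.** Protocol section 10.1 sets the model for binary outcomes, the primary composite among them: "Percentages in both arms of the study will be compared using binomial regression with a log link, adjusting for the minimization variables". The output is a risk ratio with a 95% confidence interval. The second effect measure gets one line: "Risk differences will be estimated similarly". No link is named for it; an identity link is the natural reading.

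Section 6.4.1 lists the minimisation variables. Allocation is "balanced by thrombosis (yes/no), previous adverse pregnancy outcomes (yes/no), previous pregnancy (yes/no), refractory obstetric APS (yes/no) and center". The model therefore carries four binary factors and centre. Nothing says whether centre enters as fixed effects, as a random effect or after pooling.

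Section 4.2 states: "The HYPATIA trial has been designed as a multicenter RCT". Its centre table has 17 rows. One London hospital appears twice and two Danish sites only screen, so 17 − 1 − 2 = 14 centres randomise: 7 in the UK, 4 in Denmark and one each in Italy, Ireland and Canada.

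Section 10.2 gives the planning risks as "a lower prevalence of aPL related pregnancy morbidity (47% versus 63% p=0.004" and the target: "The trial is powered to detect a 16% reduction in pregnancy morbidity". The analysed number is to be 328: "In order to achieve a number of 328 pregnant women, we will randomize 400 patients".

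Section 10.1 also says that departures from the analysis plan are not intended and would be reported if they became necessary.

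**The concern.** A log link makes each fitted risk the exponential of a linear predictor. Nothing in the link keeps that value at or below 1, so the limit acts as a constraint on the fit. When outcomes are common and the model has many terms, some combination of centre, arm and history is easily pushed against the limit. The likelihood then peaks on the edge of the allowed region. Standard iterative software may stop without converging, and a Wald standard error computed there lacks its usual justification. An identity link has the same weakness, with limits at both 0 and 1.

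The quantities at stake are the primary risk ratio and its interval. If the stated model does not fit cleanly, the analyst has to drop centre, drop a factor or change the model, and may do so knowing what each choice does to the result.

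**Working it through.** **1. Planning figures.** Inputs from section 10.2: risks 0.63 and 0.47, and "significance alpha = 0.05, power 1-beta 80%, percentage cross 5" per cent. Two-sided testing and equal arms are assumed.

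- Per arm: (1.960 + 0.842)² × (0.63 × 0.37 + 0.47 × 0.53) / 0.16² = 7.85 × 0.4822 / 0.0256 ≈ 148
- Allowing for 5% crossover: 148 / 0.95² ≈ 164 per arm, so 328 in total

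The plan's 328 is reproduced and is not in question here.

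**2. Size of the model.** Intercept 1 + treatment 1 + binary factors 4 + centre 13 = 19 parameters. Women per centre average 328 / 14 ≈ 23.

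**3. Room below a risk of 1.** Relative to the arm average, covariates may raise the fitted risk by a factor of at most 1 / 0.63 = 1.59 in the control arm and 1 / 0.47 = 2.13 in the treated arm. At a risk of 30% the factor would be 3.33. This is why the problem eases when events are less common.

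**4. How often the maximum lies on the boundary.** Trials of 328 women, 1:1, were simulated with 500 trials per setting (Monte Carlo standard error at most √(0.25 / 500) = 2.2 points). The log-binomial likelihood was maximised. A trial counted as interior only if every fitted risk was at most 1 at zero score.

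| Risks | Setting | On boundary |
|---|---|---|
| 63% / 47% | 14 equal centres, no prognostic effects | 48% |
| 63% / 47% | 14 equal centres, modest effects | 75–82% |
| 63% / 47% | 14 unequal centres | 70–86% |
| 63% / 47% | 14 very unequal centres, modest effects | 95% |
| 63% / 47% | unequal centres only, no binary factors | 53% |
| 63% / 63% | 14 centres | 44–88% |
| 45% / 35% | 14 centres | 41–59% |
| 30% / 20% | 14 centres | 21–34% |
| 63% / 47% | four binary factors, no centre | 0.4–2%; 19% with doubled effects |

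Centre is the main cause.

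**5. Assumptions.** The protocol gives no centre sizes, factor prevalences or prognostic effects, so all are assumed. Five settings were repeated (150 trials each) and checked with a constrained optimiser, which agreed on the classification in every trial. Those runs assumed:

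- thrombosis in 35%, previous pregnancy in 70%, a previous adverse outcome in 70% of the latter, and refractory disease in 30% of those;
- where effects were present, log-odds effects of 0.2 (thrombosis), 0.3 (adverse outcome) and 0.3 (refractory), with a between-centre standard deviation of 0.3;
- unequal centre sizes in proportion to 1, 1/2, …, 1/14. These sum to 3.25, so the largest centre has about 328 / 3.25 = 101 women and the smallest about 101 / 14 = 7.

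**6. What software returns.** At 63% / 47% with centre, default iterative fitting gave a converged fit with finite standard errors and all risks below 1 in 3% to 31% of the 150-trial runs. With equal centres and no effects, 50% of those trials had an interior maximum but only 31% gave a clean fit, so the algorithm can fail even where an ordinary solution exists. A further set of runs gave 6% to 39% with centre and 81% without. With unequal centres, an identity-link fit was clean in 39% (no prognostic effects) and 21% (modest effects).

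**7. Is there still an estimate?** Yes. The constrained maximum was found in every checked trial, with median risk ratio 0.74 to 0.76 at 63% / 47%. The crude ratio is 0.47 / 0.63 = 0.746.

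**8. Alternatives.**

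- Poisson regression with a log link and robust variance, on the same covariates, converged in every checked trial. Its median risk ratio was 0.75 to 0.76. The standard deviation of the log risk ratio was 0.097 to 0.117, against 0.101 to 0.121 for the constrained log-binomial. In these runs, centres with no event were removed before fitting.
- Standardised logistic regression, with centres of fewer than 10 women pooled by country, converged in 98% to 99% of trials, with median risk ratio 0.75.
- The same pooling with the log-binomial model kept gave a clean fit in only 27% (no effects) and 5% (modest effects). Pooling alone does not cure it.

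Interval coverage was not simulated. That the Wald interval is unsound at a boundary rests on standard theory.

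**The case against.** The strongest reply is that the protocol does not prescribe 13 centre indicators. A random or pooled centre effect is compatible with the text and was not simulated, and without centre the trouble nearly disappears. How centre enters, how small sites are combined and what happens after a failed fit are commonly left to the statistical analysis plan, which is not at hand. That stands, so the absence of a fallback is not the point. The point is the model that the protocol does name: read in the ordinary way, it is ill suited to the protocol's own planning risks and number of centres.

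The dependence on assumptions also stands. The failure share moves widely with unstated inputs and falls well below one half if events are less common.

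Three stronger readings are tempting, and the documents do not support them.

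- A reader might infer that the likelihood has no valid maximum and the risk ratio cannot be estimated. The likelihood is concave, and the constrained maximum was found in every checked trial. Convergence and the interval fail, not the existence of an estimate.
- A reader might add the rare secondary outcomes, where some centres will have no events. That is separation, which also gives infinite centre coefficients in a logistic model, so it is no argument against the log link.
- A reader might want lupus anticoagulant status and maternal age added to the model. The protocol gives no figures on their prognostic value, and adjusting for the variables used in allocation is a coherent choice.

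**Conclusion.** The concern holds in a conditional form. With centre as fixed effects and risks near 63% and 47%, the stated primary model would end on the boundary in roughly half to nearly all trials (48% to 95% across the assumed settings), and routine software would often return no usable fit. The standard error and 95% interval that section 10.1 relies on would then lack justification, although a point estimate would exist. The risk difference shares the problem if an identity link is meant. The conclusion rests on fixed centre effects, on event risks near the planning values, and on assumed centre sizes, prevalences and prognostic effects. The sample size of 328 is unaffected.

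**What to change.** Before unblinding, replace the model sentence in section 10.1 with one of two options, and name which is primary:

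- the risk ratio from Poisson regression with a log link and robust standard errors; or
- both the risk ratio and the risk difference by marginal standardisation after logistic regression, with delta-method or bootstrap 95% intervals.

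The second option has the merit of giving both measures from one model. Either should adjust for the four binary minimisation factors and centre.

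State how centre enters, with a rule for combining small centres that is fixed before unblinding. Combining within country is not enough, because Italy, Ireland and Canada each have a single site. The rule must say where such a site goes if it is small, for example into one joint stratum. It must also deal with centres where no woman, or every woman, has the event. At 63% / 47% with unequal centres, 5% to 47% of simulated trials had a centre of the first kind and 12% to 65% one of the second. If the statistical analysis plan already contains such a rule, the protocol sentence should be aligned with it.

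The cost is wording. The one statistical price is that small centres are adjusted for less exactly.

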10.2 Sample Size

The sample size was calculated based on our audit data.

Retrospective data from St Thomas' Hospital showed that treatment with HCQ was associated with a higher rate of live birth (67% in women with SLE and aPL treated with HCQ versus 57% in women in the control group p=0.005) and a lower prevalence of aPL related pregnancy morbidity (47% versus 63% p=0.004).

The HCQ intervention will be added to current standard of care. The trial is powered to detect a 16% reduction in pregnancy morbidity, which is the main outcome of the study (total sample size 328). A minimum of 328 women will therefore be randomized. In order to achieve a number of 328 pregnant women, we will randomize 400 patients. This takes into account those women who do not achieve pregnancy within 12 months and those who do not pregnant due to other reasons.

The calculation was made on the following: significance alpha = 0.05, power 1-beta 80%, percentage cross 5%.

11 Trial Steering Committee

A HYPATIA steering committee has been appointed. The committee includes [name], [name], [name], further HYPATIA study team members and a lay person. A dedicated person from the Clinical Trials Unit will be appointed. An independent chair will be appointed.

The overall role will be to provide overall supervision of the HYPATIA study and the steering committee will meet on a 6 monthly basis. The Steering Committee is the main decision making body. It has overall responsibility for scientific strategy and direction and has ultimate responsibility for ensuring the project's aims are delivered on time and within budget.

12 Data Monitoring Committee

A Data Monitoring Committee has been appointed. The committee includes an independent chair, an independent statistician, the trial statistician and an independent expert.

The DMC has decided the following stopping rules:

Confirmed option of unblinding available at any stage, BUT only if concern that treatment will clearly harm or benefit patients

The simple rule of 3 standard errors will be applied to difference between groups.

13 Direct Access to Source Data and Documents

The Investigator(s) will permit trial-related monitoring, audits, REC review, and regulatory inspections by providing the Sponsor(s), Regulators and REC direct access to source data and other documents (e.g. patients' case sheets, blood test reports, X-ray reports, histology reports etc.).

14 Ethics & Regulatory Approvals

The trial will be conducted in compliance with the principles of the Declaration of Helsinki (1996), the principles of GCP and in accordance with all applicable regulatory requirements including but not limited to the Research Governance Framework and the Medicines for Human Use (Clinical Trial) Regulations 2004, as amended in 2006 and any subsequent amendments and applicable local regulations in participating countries.

This protocol and related documents will be submitted for review to the South London Research Ethics Committee (REC), and to the Medicines and Healthcare products Regulatory Agency (MHRA) for Clinical Trial Authorization in the UK and to respective bodies in all participating countries.

The Chief Investigator will submit a final report at conclusion of the trial to the KHP-CTO (on behalf of the Sponsor), the REC and the MHRA (regulatory authorities of other states in which the trial is taking place) within the timelines defined in the Regulations.

15 Quality Assurance

Monitoring of this trial to ensure compliance with Good Clinical Practice and scientific integrity will be managed and oversight retained by the Good Clinical Practice (GCP) Unit (Copenhagen) and a dedicated monitor.

16 Data Handling

The Chief Investigator will act as custodian for the trial data. The following guidelines will be strictly adhered to:

Patient data will be anonymized.

- All anonymized data will be stored on a password-protected computer.
- All trial data will be stored in line with the Medicines for Human Use (Clinical Trials) Amended Regulations 2006 and the Data Protection Act and archived in line with the Medicines for Human Use (Clinical Trials) Amended Regulations 2006 as defined in the Kings Health Partners Clinical Trials Office Archiving SOP. For our EU sites: All trial data will be stored and archived according to applicable local regulatory requirements.

For blood samples obtained from women at St Thomas' Hospital/UK:

Samples will be stored linked anonymized (i.e. using participant study number) in locked freezers in the Thrombosis Research laboratory, St Thomas' Hospital. Only members of the research team have access to the samples. All laboratories are locked by the end of the day and freezers are also constantly locked. Only members of the research team have access. After 15 years of storage blood samples will be discarded.

For samples obtained from women at Danish, Irish and Canadian study sites: Samples will be stored linked anonymized (i.e. using participant study number) in locked freezers at each participating sites locally. After 25 years of storage blood samples will be discarded.

17 Data Management

A website for the HYPATIA trial will be created. All participating investigators will be given an individual access to the website in order to enter data.

A MACRO database is provided by the KCTU. Information about the patient will be kept in the in medical records and will then be transcribed into the electronic CRF (eCRF). Each patient will be allocated a participant number (which will include the study site identification and the patient number) that will be used to identify the patient, no personal data will be recorded in the database. Data in the eCRF will be filled in at each trial visit.

A separate data management plan will be created for the trial.

18 Publication Policy

It is intended that the results of the study will be reported and disseminated at international conferences and in peer-reviewed scientific journals.

19 Insurance / Indemnity

The sponsor will provide indemnity for all NHS based sites in the UK, for sites in the EU and Canada.

20 Financial Aspects

Funding to conduct the trial is provided by the NIHR Research for Patient Benefit and the NOVO Nordisk Foundation.

21 Signatures

To be signed by Chief Investigator minimum.

Chief Investigator

Date

Print name

REFERENCES:

- 1. Miyakis, S., et al., *International consensus statement on an update of the classification criteria for definite antiphospholipid syndrome (APS)*. J Thromb Haemost, 2006. **4**(2): p. 295-306.
- 2. Gardosi, J., et al., *Customised antenatal growth charts*. Lancet, 1992. **339**(8788): p. 283-7.
- 3. Gardosi, J., et al., *An adjustable fetal weight standard*. Ultrasound Obstet Gynecol, 1995. **6**(3): p. 168-74.
- 4. Tranquilli, A.L., et al., *The classification, diagnosis and management of the hypertensive disorders of pregnancy: A revised statement from the ISSHP*. Pregnancy Hypertens, 2014.
 4(2): p. 97-104.
- 5. Parke, A.L., *Antimalarial drugs, systemic lupus erythematosus and pregnancy.* J Rheumatol, 1988. **15**(4): p. 607-10.
- 6. Parke, A., Antimalarial drugs and pregnancy. Am J Med, 1988. 85(4A): p. 30-3.
- 7. Ostensen, M., et al., *Anti-inflammatory and immunosuppressive drugs and reproduction*. Arthritis Res Ther, 2006. **8**(3): p. 209.
